The University of Texas Southwestern Medical Center at Dallas Institutional Review Board

Protocol Template (for Investigator Initiated Studies)

Title: A PROSPECTIVE, RANDOMIZED, DOUBLE-BLIND, SHAM-CONTROLLED STUDY OF THE LOW-LEVEL PHOENIX THERA-LASE 42 WATT LASER IN PATIENTS WITH CHRONIC FIBROMYALGIA

1. Introduction and Purpose:

Individuals who have had pain for greater than three months may exhibit widespread pain and hypersensitivity, making it challenge to resolve or manage the condition, and resulting in impaired biological, social, and psychological function. The use of various laser or light devices is an evidence based approach for treating common musculoskeletal conditions that can assist in decreasing inflammation, improving tissue metabolism, and improving pain, hypersensitivity, and physical function.

The purpose of this study is to examine the use of low level therapeutic laser (LLLT) for its effects on pain, fatigue, and physical function in individuals with fibromyalgia.

2. Background:

Fibromyalgia is a common chronic pain syndrome that is often refractory to available treatments. The syndrome is characterized by chronic fatigue, painful muscles and tender points which commonly present bilaterally in a symmetrical pattern in the posterior cervical and thoracic back areas. Recent advances in non-thermal therapeutic laser technology (termed low level laser therapy- LLLT) have introduced possible clinical advantages that would potentially impact wide-spread chronic pain conditions like fibromyalgia. These advances include greater light power outputs, allowing for therapeutic doses to be clinically applied in larger areas of symptoms as is typical in individuals with fibromyalgia. The potential of this higher power light therapy is to decrease the inflammation and irritability of the sympathetic nervous system, and improve local biochemical and metabolic support in the musculoskeletal tissues. Clinically, laser therapy has the potential to effectively relax muscle tender points and relieve pain, thereby reducing global discomfort and improving overall quality of life.

The manufacturer of the Phoenix Thera-lase elected to seek and was awarded FDA approval under "Sec. 890.5500 Infrared lamp." The election of this classification selection was based primarily on the type of photonic energy provided which is in fact infrared light and the purpose of the superficial topical application. The product codes available for this section include a wide variety of applications, including "Lamp, Infrared, Therapeutic Heating," and "Powered Laser Non-Thermal Instruments With Non-Heating Effects For Adjunctive Use In Pain Therapy." The lower powered infrared therapeutic laser is significantly different than other medical lasers which utilize much higher power and have a purpose of altering tissue anatomy through high thermal or mechanical energy conversion. Lower power therapeutic laser therapy, as with the device used in this study, works through a conversion of the photonic energy of specific wavelengths and power to provide photochemical (biochemical) changes within the diversity of tissues that absorb the light. As such, the clinical benefits of therapeutic laser therapy in the infrared range is widely used for tissue repair, pain reduction, and resolution of inflammation, and is not attributed to the excessive production of thermal energy. The perception of a warming effect is very superficial and associated with water in the superficial layers absorbing energy. This is similar to the feeling that occurs with other infrared devices.

3. Concise Summary of Project:

Fifty consenting participants with long-standing fibromyalgia (> 3 mo duration) will be randomized to one of two treatment groups (n=25 per group) according to a computer generated randomization table. Group 1 will be the 'sham' control group and Group 2 will be the 'active' laser treatment group.

The study will be conducted in a double-blind fashion using a standard 42 watt Class IV laser which has a switch at the back of the device which allows the laser to operate in the 'inactive' mode despite giving the operator and patients the appearance of being active (e.g., generates skin warmth and a red beam of light). Treatment will be administered three times/week for three weeks. Data will be collected across the 3-week intervention and at one week and one month after completion of the intervention. Data will be analyzed with appropriate statistical methods.

4. Study Procedures:

Potential participants will be identified through physician referral to the McDermott Center for Pain Management, as well as through advertisement via the UT Southwestern Campus Updates email blast. If participants meet screening criteria and are willing to participate, appropriate consent and HIPPA permissions will be obtained.

After consent, the participant will complete baseline outcome assessments and will be randomized to one of the two treatment cohorts, the experimental low level laser therapy group (LLLT), or the sham laser therapy group (Sham). The study investigator performing outcome assessments will be blinded to the treatment allocation group. The treating clinician will be aware of the treatment allocation assignment for laser application; however, the participant will remain blinded to the treatment cohort. Each treatment cohort will be completed as assigned—no crossover will be allowed. Each participant will receive a series of nine active laser or sham treatments on a M-W-F schedule over the three week treatment period.

The treatments will include multiple 60 sec applications over the bilateral sympathetic ganglion in the paraspinous region from T1-S2. To address the question of depth and localization of treatment, we propose that multiple tissues are being stimulated simultaneously with the application of the infrared light, including muscle, tendon, ligament, joint, and nerve. The reference to the treatment being applied over the sympathetic ganglion was not intended to suggest a primary focus of treating this structure, but rather, to standardize an anatomical landmark for where we could apply the laser treatment with the potential to stimulate the greatest number of tissues (paraspinal muscle and tendon, spinal zygapophyseal and costotransverse ligaments and joints, and sympathetic and peripheral nerves) within this region based on the superficial depth of penetration of infrared lasers of this power. Additionally, evidence supports the ability of infrared light to stimulate and positively affect the sympathetic ganglion in the lumbar spine, where the nerves are only 1 cm below the skin surface (Muneshige et al., Journal of Rehabilitation Research & Development, 2006).

Additionally, participants will receive treatment over any tender spots reported in the hips, knees, shoulder, or elbows. Total treatment time to the spine will range from 12-14 minutes, depending on the size of the subject. Total treatment time to extremity joints will not exceed two minutes per site, so that the total treatment time to the spine and extremities will not exceed 30 minutes. All treatment for the LLLT group will be delivered at an intensity of 42 watts. The treatment will be applied via a non-contact method, with the laser applicator held 15 inches above the participant's skin. Sham treatment will be delivered via the same protocol in terms of time, application, and areas of treatment as stated above, except the laser unit will not discharge any photonic energy. Intervention will take place in the therapy room at the Health Professions Physical Therapy Clinic, which is appropriately equipped for laser administration. Application of therapeutic laser will be completed by licensed physical therapists who have completed safety training for therapeutic laser application including appropriate use of safety eyewear, room access, laser signage for laser use, and patient monitoring.

The following outcome measures will be collected at baseline: (1)Standardized SF-36 questionnaire; (2) Symptom Impact Questionnaire; (3) Current analgesic medication usage; (4) Pressure-pain threshold testing over tender points; and (5) Spinal ROM with an inclinometer and accelerometer. Outcome measures (2) and (3) will be re-assessed during the treatment phase at the end of weeks 1, 2 and 3. At 1 week and 1 month after the last laser/sham treatment session, all baseline assessments will be repeated, in addition to a global rating of change scale (-7= very harmful, 0=

neutral, +7 = very helpful). Any patient who reports any harm from the laser/sham treatments on the helpfulness scale will be queried for specific harm details. Participants randomized to Sham will have the option of receiving LLLT treatments after they complete their study enrollment.

5. Sub-Study Procedures:

Not applicable for this study.

6. Criteria for Inclusion of Subjects:

- 1) 18-80 years old
- 2) Pre-existing medical conditions are under stable control
- 3) Diagnosis of fibromyalgia by standard criteria (e.g., pain in all four body quadrants for over 3 months, 11 of 18 tender points, bilaterally in the cervical and upper thoracic back areas, and chronic fatigue)
- 5) Able to wear laser protective eyewear during the treatment session
- 4) Ability to speak English and complete testing

7. Criteria for Exclusion of Subjects:

- 1) Presence of another pain syndrome that has anatomical overlapping with fibromyalgia pain
- 2) Unstable psychiatric disorders or cognitive dysfunction or serious memory impairment
- 3) Previous treatment with low level laser therapy
- 4) Contraindication to receiving laser treatments
- 5) Current use of photosensitive medication (has been instructed to minimize sun exposure)
- 6) Active metastasis
- 7) Active infection
- 8) Impaired sensation

8. Sources of Research Material:

Subject's research data will be obtained from the medical record and self-report questionnaires. Other data generated during testing (all outcome measures) will be sources of research material. All research material will be kept in a separate paper chart that will include demographic information including height, weight, age, gender, location and side of involvement, and self-report outcome measures. The paper chart will also include all objective outcome measures including the SF-36, Symptom Impact Questionnaire, global rating of change scale, and analgesic medication usage questionnaire.

9. Recruitment Methods and Consenting Process:

All participants will be recruited either from physician referrals to the multidisciplinary pain clinic or from self-referrals in response to an advertisement in Campus Updates. During the initial screening visit, one of the co-investigators will determine if the subject's condition matches the inclusion and exclusion criteria. If so, the study will be briefly described and the subject will be asked verbally if they would be interested in volunteering to participate in the study. It will be explained to subjects that participation is completely voluntary, and choosing to not participate will not impact their receipt of other medical services on campus. An affirmative verbal response will then be followed by either the PI or Co-PI obtaining written informed consent to participate and signed authorization for use and disclosure of health information gathered during the examination. They will explain the study with the written documents and answer any questions the potential subject may have. After all questions are answered, if the potential subject elects to participate, the consent forms will be signed. Subject's privacy of all private health information and study measurements will be maintained according to the UTSW standard clinical practices (within the EPIC EMR). Any electronic or paper recording of study measures will kept either on approved encrypted storage devices or locked in a secure file cabinet. Competence in the English language is an inclusion criteria for the study.

10. Potential Risks:

Primary risks or side effects of participating in this study are globally associated with the entry requirement of having a musculoskeletal condition with chronic pain. Primary risk of the study specific intervention (therapeutic Class IV laser, 42 watts) includes potential eye injury if direct contact is made without proper eye wear. All personnel involved with this study have completed safety training on proper use of all personal and environmental safety steps including use of safety eye wear for therapeutic laser application. Therefore, there is minimal risk overall with included protocols. Low level laser therapy has been used daily in our outpatient clinic for over 3 years with no adverse events or safety issues. The study intervention is standard of care in rehabilitation and could be implemented with participants regardless of study participation. All of these risks are typical with standard of rehabilitation care and manageable. There is also a potential loss of confidentially of the patient's medical information.

11. Subject Safety and Data Monitoring:

Tests and interventions used in this study represent standard procedures and care delivered by physicians and licensed physical therapists. A supervising physical therapist (blinded investigator) will be responsible for evaluating all patient complaints outside the usual presentation for medical disposition. A study physician will be informed of all patient complaints outside the usual presentation for medical disposition. The treating therapist will ensure that all participants' evaluation is consistent with standard practice.

12. Procedures to Maintain Confidentiality:

Information used in the data analysis from this research project will be transferred by the principal investigator from the patient's medical record to a written data analysis form that will be identifiable only by a subject number. Each subject's information will be labeled with a unique number identifier to avoid mixing records and to ensure confidentiality. Only the principal investigator will have access to the number key that would identify each individual subject. Subject's privacy of all private health information and study measurements will be maintained according to the UTSW standard clinical practices (within the EPIC EMR). Any electronic or paper recording of study measures will stored either on approved encrypted storage devices or locked in a secure file cabinet with the clinic department. All data derived from the investigation is only accessible by the investigative team. Medical chart information is secured by username and password access to the EPIC EMR per university policy.

13. Potential Benefits:

This clinical investigation will evaluate the use of Class IV therapeutic laser in the treatment of fibromyalgia. While the data generated by the participants will not specifically benefit them individually beyond their physical improvement, the information gathered from this study will assist the medical profession in treating chronic pain conditions in the future as well as provide a basis for future research.

14. Biostatistics:

Evaluation of the a-priori sample size was calculated utilizing a power analysis. This analysis was based on the primary outcome measure (pain) being a continuous response variable. Data from previous published research on the projects primary intervention conducted over longer periods of treatment time supports an effect size of 0.4 on the impact of Class III light therapy techniques. Power calculations for the current project were based on mean differences between two dependent groups (matched pairs), power (1- β probability) = 0.80, α error probability = 0.05, and effect size of 0.4 (GPower ver. 3.1). These parameters resulted in a total sample size calculation of 52 to reject the null hypothesis. Accounting for a dropout rate of no more than 15%, a final sample size of 60 was selected. Dependent variables will be evaluated with non-parametric analysis for reports of patient well-being, while repeated measure ANOVAs will be utilized for changes of significance over time in pain, quality of life, function, ROM, and pressure-pain threshold. Significance will be set at p<0.05.

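### Two planned sample sizes: 50 (25 per group) in Section 3 and 60 in Section 14, and 50 is below the calculated requirement of 52

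*Combined protocol and SAP*

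**What the plan says.** Section 3 (Concise Summary of Project) sets the size of the trial as "Fifty consenting participants with long-standing fibromyalgia (> 3 mo duration) will be randomized to one of two treatment groups (n=25 per group", and links those group sizes to a computer-generated randomisation table.

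Section 14 (Biostatistics) gives a different total. Its calculation is "based on mean differences between two dependent groups (matched pairs"), with "power (1- β probability) = 0.80" and "α error probability = 0.05, and effect size of 0.4 (GPower ver. 3.1"). The result is reported as follows: "These parameters resulted in a total sample size calculation of 52 to reject the null hypothesis". The next sentence inflates it: "Accounting for a dropout rate of no more than 15%, a final sample size of 60 was selected".

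Both statements are current text. No section says that one replaces the other, or explains how 50 relates to 60.

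**The concern.** The protocol has two enrolment targets in force. The lower one is under the figure that its own calculation says is needed, before any participant is lost, and so it leaves no allowance for dropout.

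Three things depend on this number: the length of the randomisation list, the point at which enrolment ends, and the planned size against which the final report will be read. The protocol describes no interim analysis and no other rule for ending enrolment, so the planned total is the only such rule. With two totals on the page, stopping at 50 and continuing to 60 could each be described as following the protocol. The ethics board also cannot tell how many people it is approving. Finally, a reader of Section 14 would credit the trial with 80% power, which a trial run to Section 3 would not have.

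**Working it through.** **Inputs.** From Section 3: 50 randomised, 25 per group. From Section 14: paired comparison, effect size 0.4, α = 0.05, power 0.80, required total 52, dropout at most 15%, final total 60. Section 14 does not say whether the test is one-sided or two-sided.

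**Step 1: reproduce 52.** For a two-sided paired t-test with n pairs and standardised difference d, the test statistic is noncentral t with n − 1 degrees of freedom and noncentrality d√n. Power is the probability that it falls outside ± the 97.5% point of the central t distribution.

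- n = 51: noncentrality 0.4 × √51 = 2.86, power 0.7999
- n = 52: noncentrality 0.4 × √52 = 2.88, power 0.808

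The smallest n reaching 0.80 is 52, which is the protocol's figure. A one-sided test would need only 41, so the two-sided version is the one that was used.

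**Step 2: reproduce 60.** 52 × 1.15 = 59.8, rounded up to 60. The more usual form, 52 / (1 − 0.15) = 61.2, gives 62. The gap of two is minor, but it means that 60 × 0.85 = 51 completers, one fewer than 52.

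**Step 3: put both totals on the same basis.**

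| Randomised | Dropout | Completers | Power (paired, two-sided, d = 0.4) |
|---|---|---|---|
| 50 | none | 50 | 0.792 |
| 50 | 15% | 42.5, taken as 42 | 0.716 |
| 50 | 15% | 42.5, taken as 43 | 0.727 |
| 60 | none | 60 | 0.862 |
| 60 | 15% | 51 | 0.800 |

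Against the required 52, a trial of 50 starts 2 short and ends 9 to 10 short at 15% dropout. A trial of 60 can lose 8 participants (8/60 = 13.3%) before it falls below 52.

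**Step 4: look for a reading that reconciles the totals.**

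- 50 as the completers expected from 60: Section 3 says the fifty are to be randomised, and 60 × 0.85 is 51.
- 60 as the number screened or consented: Section 14 ties 60 to dropout, and the fifty in Section 3 have already consented.
- 50 as a rounded 52: Section 3 gives exactly 25 per group, and 52 is itself before dropout.

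None of these fits the text.

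**The case against.** The strongest reply is that this is an inconsistency of wording with a small effect on power. No calculation in Section 14 is wrong: 52 reproduces exactly, and 60 follows from it. With complete follow-up, 50 gives 79.2% against 80.8% at 52, a loss of 1.6 points. The fall to 71.6% needs the full 15% dropout, which the protocol gives as a ceiling and not as an expectation. Sixty also misses 52 slightly, since it leaves 51. Nothing in the text suggests that anyone intends to choose the stopping point after seeing results, and the outcome assessor is to be blinded.

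Much of this is fair. The 42 completers should be read as the worst case that the protocol allows for. The shortfall with no dropout is small. Choosing the stopping point on the basis of results is a possibility that the text leaves open, not something it describes. That 52 means participants with outcome data is an inference, though a natural one because dropout is added on top of it.

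The reply does not remove the contradiction. The protocol still gives two totals, and only one of them meets the stated power at the stated dropout limit: 60 gives 0.7999, which is 80% for any practical purpose, while 50 gives about 72%.

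**Conclusion.** The concern holds. The planned size is stated as 50 in one section and 60 in another, a difference of 10 participants, with nothing to say which governs. On the protocol's own calculation, a trial of 50 falls short of 80% power by 0.8 points with no dropout and by about 8 points at 15% dropout.

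These figures assume a two-sided test, inferred because it is what yields 52, and they take the protocol's paired formula and effect size of 0.4 at face value. That formula is itself doubtful for two independent groups. If 0.4 is a between-group standardised difference, which the protocol does not say, power from a two-sided two-sample t-test would be about 28% at 25 per group and 33% at 30 per group, and 80% would need 100 per group. That is a separate defect. It means that choosing between 50 and 60 does not by itself give adequate power for the comparison of laser with sham, but the protocol must still commit to one number.

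This should be corrected, because the planned sample size is a core design parameter and the conflict is plain in the current text.

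**What to change.** State one randomised total and one per-group number, identical in Sections 3 and 14, and generate the randomisation list for that total.

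- **If 60 is the target:** change Section 3 to 60, with 30 per group, and say that 15% dropout leaves 51. To keep 52 after 15% dropout, 62 would be needed (62 × 0.85 = 52.7).
- **If 50 is the target:** remove the final size of 60 from Section 14. State that completers could be as few as about 42 at the dropout ceiling, and give the resulting power on the current formula: 79% with no dropout, 72% at 15%.

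In either case, state in Section 14 that the test is two-sided. It would be sensible to settle the number together with any revision of the matched-pairs basis, so that the total is changed only once.

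The cost is a short amendment. Keeping 50 makes the stated power less favourable; keeping 60 means 10 more participants than Section 3 now provides for.

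### Does the protocol describe two different shams, one that shows a red beam and one that emits nothing?

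*Combined protocol and SAP*

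**What the plan says.** Section 3 describes a switch at the back of the device. In its inactive setting the unit does not treat, despite "giving the operator and patients the appearance of being active (e.g., generates skin warmth and a red beam of light").

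Section 4 describes the sham as equal to active treatment in duration, technique and sites, "except the laser unit will not discharge any photonic energy". The same section gives the treatment distance, "with the laser applicator held 15 inches above" the skin without contact, and sets the active arm at 42 watts. It also says that the treating clinician knows the allocation; "however, the participant will remain blinded to the treatment cohort".

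Section 2 explains the device's regulatory class by "the type of photonic energy provided which is in fact infrared light", and later attributes the therapeutic action to photonic energy of particular wavelengths and power. On heat it says: "The perception of a warming effect is very superficial and associated with water in the superficial layers absorbing energy". Section 4 likewise describes the mechanism as infrared: "multiple tissues are being stimulated simultaneously with the application of the infrared light".

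No section gives a power, wavelength, irradiance or skin temperature for the inactive mode.

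**The concern.** The sham is the whole comparator, and its two descriptions do not match word for word. A unit that projects a red beam discharges some photonic energy in the ordinary sense, and Section 4 says it discharges none of any kind. The warmth is also puzzling: the applicator is 15 inches away, and the only account of warming is given for the therapeutic laser.

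Two things could be at stake. If Section 4 is literal, sham participants lack the beam, and possibly the warmth, that Section 3 relies on to make the inactive mode look active. They might then guess their arm, and most of the outcomes are self-reported. If Section 3 is literal, the control emits something, and a report calling it a zero-output sham would misdescribe it.

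**Working it through.** No power, alpha or sample-size figure enters this point, so the check is a comparison of the texts plus a count of what the description touches.

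**1. How the protocol uses the term.** Photonic energy appears three times: twice in Section 2 and once in the disputed sentence of Section 4. Both uses in Section 2 concern the therapeutic agent, and the first identifies it as infrared. Carried into Section 4, that meaning makes the sentence say that the sham withholds the therapeutic output.

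**2. The three readings side by side.**

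| Reading | Red beam in sham | Warmth in sham | Sections 3 and 4 | Consequence |
|---|---|---|---|---|
| Term means therapeutic infrared | Present | Source not stated | Compatible on the beam | None shown |
| Section 4 literal (no light at all) | Absent | In doubt | Section 3 wrong | Possible unmasking |
| Section 3 literal, term means all light | Present | Present | Section 4 wrong | Control misdescribed; no treatment effect documented |

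The first reading is the only one that needs no error in either section as regards the beam. It does not account for the warmth. That is a missing explanation and not a second contradiction, because Section 2's account of warming does not address the inactive mode.

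**3. Extent.**
- Sham participants: 25 of 50 by Section 3. Section 14 (Biostatistics) selects 60; assuming equal allocation, that would be 60 / 2 = 30. The two totals disagree, but that is a separate matter.
- Sessions per participant: 3 per week × 3 weeks = 9.
- Outcome measures: 5 at baseline, and at follow-up "all baseline assessments will be repeated, in addition to a global rating of change scale", so 5 + 1 = 6. Questionnaires or ratings are the SF-36, Symptom Impact Questionnaire, analgesic use and global rating of change: 4 of 6. The other two are pressure-pain threshold and spinal range of motion.

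The 4 of 6 counts instruments and does not measure bias. Section 14 names pain as primary without tying it to one of these instruments, and pressure-pain threshold also depends on the participant's response.

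**4. How exposed masking is if Section 4 is literal.** Participants have had no previous low level laser therapy (Section 7), must be able to wear protective eyewear (Section 6) and do not cross over (Section 4). They therefore have no personal experience of active treatment to compare with. On the other side, Section 7 excludes impaired sensation, so warmth or its absence can be felt. Nor can it be assumed that treatment stays out of view on the back. With 12 to 14 minutes on the spine and a 30-minute cap, extremity time can reach 30 − 14 = 16 to 30 − 12 = 18 minutes, more than half the session.

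**5. Size.** Without an inactive-mode output, neither a sham dose nor a bias from unmasking can be calculated.

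**The case for a change.** The strongest case for acting is that the control condition should not need interpretation. Section 4 excludes photonic energy of any kind and does not limit this to infrared. No sentence expressly applies the narrower meaning to the sham, and that meaning still leaves the warmth without a source. Section 3 names warmth and beam as what makes the inactive mode look active, and Section 4 promises that participants stay masked. Checking the device specification before enrolment is cheap, whereas an unclear sham can afterwards only be reported as a limitation.

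Part of this stands. The wording is loose, the warmth is unexplained, and a definition of the term would help readers. The mitigating facts reduce the risk of unmasking but do not abolish it. What does not stand is the step from loose wording to a defect in the design. The disputed sentence is itself about the sham, so the Section 2 meaning of its term applies to the sham directly. An active appearance and no therapeutic discharge are aims that one switch can meet. The missing output figure may be settled by the device specification, which is not among the documents.

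**Conclusion.** The concern does not call for a change. The two sections differ in wording, but they fit together if photonic energy means the therapeutic infrared output, as it does elsewhere in the protocol. Staff running the trial will use the switch as built, whichever sentence describes it better. Clarifying the term and confirming which sensory cues remain in inactive mode would be a minor editorial step. It would leave the device, sham, masking procedure, visits, sample size and analysis unchanged. If the cues proved absent, that would be reported as a limit on participant masking.

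The description applies to all sham participants, but no effect on results is demonstrated and none can be computed. This conclusion assumes that the term carries its Section 2 meaning into Section 4 and that the inactive mode does show the beam Section 3 describes. The documents confirm neither beyond their wording. The separate conflict over whether the treating clinician is masked plays no part in it.

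### Harm details are actively sought only from participants who report harm on one net rating after treatment ends; all other harms depend on volunteered complaints, with no stated recording or by-arm reporting

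*Combined protocol and SAP*

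**What the plan says.** Section 4 (Study Procedures) schedules the assessments.

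- **During treatment.** "Outcome measures (2) and (3) will be re-assessed during the treatment phase at the end of weeks 1, 2 and 3". Items (2) and (3) are the Symptom Impact Questionnaire and current analgesic use. Neither asks about harm from the treatment.
- **After treatment.** "At 1 week and 1 month after the last laser/sham treatment session, all baseline assessments will be repeated", and at these two visits a "global rating of change scale (-7= very harmful, 0" neutral, +7 very helpful) is added.
- **Harm inquiry.** "Any patient who reports any harm from the laser/sham treatments on the helpfulness scale will be queried for specific harm details".
- **At sessions.** The therapists' safety training is described as "including appropriate use of safety eyewear, room access, laser signage for laser use, and patient monitoring". No question to the participant and no form is described.

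Section 11 (Subject Safety and Data Monitoring) gives a second route. "A supervising physical therapist (blinded investigator) will be responsible for evaluating all patient complaints outside the usual presentation for medical disposition". It adds: "A study physician will be informed of all patient complaints outside the usual presentation for medical disposition".

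Section 8 (Sources of Research Material) lists the contents of the research chart: "paper chart will also include all objective outcome measures including the SF-36, Symptom Impact Questionnaire, global rating of change scale", and analgesic use. It lists no adverse-event or complaint record. Section 14 (Biostatistics) names the variables to be analysed, and harms are not among them.

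**The concern.** The scale has no separate harm item, so harm and benefit are netted into one number. On the natural reading, reporting harm on it means scoring below 0. A participant who had a skin reaction or a pain flare but felt better overall would score 0 or above and would not be asked for details. Nobody is asked at the nine sessions, and someone who leaves the study before the first follow-up visit never sees the scale.

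Whether the query reaches a harm thus depends partly on how much benefit the participant perceives. If the active laser is perceived as more helpful than sham, under-capture could be greater in the active arm. Section 10 already describes the risk as minimal. A low harm count from this rule would be weak support for that statement, and harms not asked about at the time are hard to recover later.

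**Working it through.** The plan states no harm rate and no capture figure, so there is no figure of its own to reproduce. The point rests on the text. The arithmetic only illustrates scale.

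**Step 1. Set the two routes side by side.**

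| Feature | Section 4 query | Section 11 complaints |
|---|---|---|
| Who starts it | Study staff, after a rating on the harmful side | The participant, by complaining |
| When | 1 week and 1 month after the last session | Any time |
| Depends on the rating | Yes | No |
| Filter | Net score | Complaint judged unusual for the condition |
| Stated purpose | Obtain harm details | Medical disposition |
| Stated recording or by-arm report | None | None |

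**Step 2. Follow three harms through the plan.**

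- *Skin reaction in week 2, final rating +4.* The query is not triggered. If volunteered, the complaint plainly falls under Section 11. If not volunteered, nothing asks for it.
- *Pain flare in week 1, final rating 0.* The query is not triggered. The Symptom Impact Questionnaire and analgesic use at the end of week 1 may show worsening, but not as an attributed or counted event. Widespread pain is an entry criterion (Section 6), so under Section 11 a flare may be judged usual.
- *Harm followed by leaving the study in week 2.* There is no rating and therefore no query, and no question at withdrawal is described. Section 11 applies only if the participant complains.

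**Step 3. Illustrate the query route alone.** The inputs are:

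- arm size n = 25 (Section 3), or 30 (half of the 60 in Section 14, assuming equal allocation);
- share lost before the rating d = 0.15, borrowed from the all-cause dropout allowance in Section 14;
- share q of harmed participants who reach the scale and still rate 0 or above at both visits. This is assumed, from 0 to 0.75;
- true harm rate r. This is assumed, 5% or 10%.

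Share of harmed participants not reached: m = d + (1 - d) × q.

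- q = 0: m = 0.15
- q = 0.25: m = 0.15 + 0.85 × 0.25 = 0.3625
- q = 0.50: m = 0.15 + 0.85 × 0.50 = 0.575
- q = 0.75: m = 0.15 + 0.85 × 0.75 = 0.7875

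Chance of recording at least one case: P = 1 - (1 - r(1 - m))^n. For example, with r = 0.10, m = 0.575 and n = 25, P = 1 - (1 - 0.0425)^25 = 0.662.

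| m | r = 10%, n = 25 | r = 10%, n = 30 | r = 5%, n = 25 | r = 5%, n = 30 |
|---|---|---|---|---|
| 0 (full capture) | 0.928 | 0.958 | 0.723 | 0.785 |
| 0.15 | 0.891 | 0.930 | 0.662 | 0.728 |
| 0.3625 | 0.807 | 0.861 | 0.555 | 0.622 |
| 0.575 | 0.662 | 0.728 | 0.415 | 0.475 |
| 0.7875 | 0.415 | 0.475 | 0.234 | 0.274 |

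Loss alone (m = 0.15) costs little. The size of the problem is driven by q, on which the documents give no information.

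**The case against.** The strongest reply is Section 11. It is not limited by timing, rating or completion of a visit. A skin or eye symptom is clearly unusual for fibromyalgia, so if the participant mentions it, the plan covers it during treatment, in someone who feels better overall, or before dropout. The Symptom Impact Questionnaire and analgesic use are also collected from everyone each week and bear on pain flares. Therapists are trained to monitor patients.

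This stands against one tempting inference, that harms outside the Section 4 trigger are simply missed. The documents do not support that: such harms are not systematically asked for, which is different. It does not remove the gap. Section 11 waits for a complaint, filters it by what is usual in a population with chronic widespread pain, and ends in clinical disposition with no stated route into the trial data.

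Three further points are fair.

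- The cut-off below 0 is the natural reading but is not defined.
- Follow-up is timed from the last session, so someone who stops treatment early but stays in the study could still be rated. The 15% allowance is also for all causes.
- A reader might infer that the safety comparison is biased in favour of the device. That would require the laser to be perceived as more helpful than sham, which is the open question of the trial, and Section 14 plans no safety comparison. Only the conditional statement holds.

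**Conclusion.** The point holds as a weakness in how harms are ascertained. The only scheduled request for harm details depends on a net rating given after treatment. The remaining route is passive and filtered, and no step is stated for recording harms or reporting them by arm. A uniform question at existing visits is plainly better and cheap, so the change should be made before data collection.

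The size cannot be fixed from the documents. For a 10% harm rate and n = 25, the chance that the query records at least one case runs from 0.93 with full capture, to 0.89 if 15% of harms are missed, to 0.66 if 57.5% are missed. These figures rest on assumed values of r and q, and on applying the overall dropout allowance to harmed participants. They give Section 11 no capture at all, so they describe the query alone and should not be read as forecasts of what the trial would record.

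**What to change.** **Section 4.** Keep the follow-up query for anyone who rates on the harmful side, and state the score that triggers it. Add one identical scripted question on any new or worsened symptom, for every participant in both arms, whatever the rating and whatever the participant thinks the cause is. Ask it on a short self-completed form at treatment visits (at least weekly), at withdrawal, and at the 1-week and 1-month visits. Self-completion matters because Section 4 says the treating clinician knows the allocation, although Section 3 suggests that the operator may be masked.

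**Sections 8 and 11.** Add the form to the research chart, and state that complaints handled under Section 11 are also entered there.

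**Section 14.** Report the number and percentage of participants with at least one event by arm, with exact 95% confidence intervals.

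These changes concern measurement only and leave treatment and clinical handling as they are.

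**Cost.** Weekly use gives 3 + 2 = 5 forms per participant, or 250 for 50 participants and 300 for 60. Use at every session gives 9 + 2 = 11, or 550 and 660. Withdrawal forms come on top. No extra visits are needed, but someone must review the forms, and more minor or unrelated symptoms will be recorded. One table is added to the report.
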